### 3.6 Demographics and Other Baseline Characteristics

Descriptive summary statistics of demographic and other characteristics (Age, Sex, Race, Ethnicity, Height, Weight, and Fitzpatrick Skin Type) list characteristics inside parentheses) will be generated for All Enrolled Population. The n, mean, standard deviation, median, minimum, and maximum and/or frequency distributions will be reported, as appropriate.

### **3.7 Wart Characteristics at Study Entry and During the Study**

Wart characteristics at study entry will be summarized descriptively for Enrolled Subjects. Summarized variables include identification of warts, wart dimension, and location (Hands, Feet, Elbows, Knees, Rest of Body). Wart Characteristics are also summarized during the study by treatment cycles for the Safety Population.

### **3.8 Prior and Concomitant Medications, Therapies and Procedures**

Prior and concomitant medications are listed only. The period(s) (prior, on treatment, and post-therapy) in which the medications were administered will be flagged. These rules are explained in Data Handling and Programming Specification Document in detail. Medications are coded using the WHO Drug (March 2019).

### **3.9 Protocol Violations**

Protocol violations will be identified prior to database lock to measure adherence to key aspects of the protocol (see Section 15 of the protocol for full definitions). Specific data fields that will be examined to identify protocol violations include inclusion/exclusion criteria and prohibited prior and concomitant medications as well as all deviations identified by the investigator. All protocol violations will be listed.

### **3.10 Efficacy Endpoints**

The primary and secondary efficacy analyses will be carried out on the Safety Population. Efficacy summaries will be supported by listings.

Primary Efficacy Endpoint: Proportion of subjects who achieve complete clearance (PWA=0) of all identified warts at each analysis visit window by treatment group and treatment cycle.

Four secondary efficacy endpoints are:

- Durability of response: For subjects with all warts achieving a status of Clear (PWA=0), the number of weeks all warts remain clear by treatment group and treatment cycle.
- Mean per-subject percent of treated warts that are Clear (PWA=0) at each analysis visit by treatment group and treatment cycle.
- Proportion of subjects with a single wart at baseline whose wart is Clear (PWA=0) by analysis visit, treatment group, and treatment cycle.
- Median time to achieve onset of Clearance (PWA=0) for all treated warts by treatment group and treatment cycle.

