4.2. Study Rationale

The rationale for the dose selection and treatment design of A-101-WART 301 and A-101-WART-302 and this open label, long term safety study is based on data collected from three completed (3) Phase 2 studies which assessed dose response and dose frequency of A-101 (H_2O_2) Topical Solution in patients with common warts. All three studies demonstrated good efficacy and safety of H_2O_2 45% for the treatment of common warts.

The three studies conducted are identified below and they represent data collected from 406 subjects.

- **Study A-101-WART-201:** A Randomized, Double-Blind, Vehicle-Controlled, Parallel- Group, Study of A-101 Solution in Subjects with Common Warts (n=90).
- **Study A-101-WART-202:** A Randomized, Double-Blind, Vehicle-Controlled, Parallel Group Study of A-101 Topical Solution Applied Once a Week in Subjects with Common Warts (n=157).
- **Study A-101-WART-203:** A Randomized, Double-Blind, Vehicle-Controlled, Parallel Group Study of A-101 Topical Solution Applied Twice a Week in Subjects with Common Warts (n=159)

Aclaris Therapeutics, Inc.

Protocol Number: A-101-WART-303

Protocol: Version 3: 14 February 2019

On the basis of these successful Phase II studies, Aclaris has progressed to phase III with studies A-101-WART 301 and A-101-WART-302. These studies will assess efficacy and safety of 8 weeks of treatment and 12 weeks of post treatment follow up. Aclaris recognizes that many patients may require multiple treatment courses and there is therefore a need to assess the long-term safety of topical H₂O₂ 45%. A-101-WART-303 is therefore designed to assess the long-term safety of patients who were initially treated in studies A-101-WART-301 and A-101-WART-302.

Aclaris Therapeutics, Inc.

Protocol Number: A-101-WART-303

Protocol: Version 3: 14 February 2019

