6. STUDY DESIGN

This is a phase 3, open label, long term safety study of A-101 Topical Solution 45% in subjects with common warts.

In order to be eligible for A-101-WART-303, subjects must have completed protocol treatment on either the A-101-WART-301 or A-101-WART-302 study.

Subjects that have complete clearance of all warts at the end of A-101-WART-301 or A-101-WART 302 may enter into the A-101-WART-303 study following completion of the Visit 1 assessments. These subjects will be followed every 6 weeks to assess for a recurrence or development of new common warts. If a recurrence occurs or a new wart develops these subjects may return to the investigational site to receive A-101 Topical Solution 45% twice a week for an additional 8 weeks.

Subjects that have warts that have not cleared (or were not treated) at the completion of A-101-WART-301 or A-101-WART 302 may enter into the A-101-WART-303 study following completion of the Visit 1 assessments will receive A-101 Topical Solution 45% twice a week for 8 weeks. Subjects may continue to receive A-101 Topical Solution 45% twice a week for 8 weeks if their warts are not clear at the end of the 8-week treatment period but the 8 weekly treatments must be initiated by Day 122.

Visit 1 of A-101-WART-303 can be the same day as Visit 13 of either A-101-WART-301 or A-101-WART 302.

All subjects will be required to remain on study for a total of 6 months.

During the study, the investigator may identify from 1 to 6 common warts (during a 8 week treatment period) to be treated twice a week for up to 8 weeks (maximum of 16 treatment applications). An 8-week treatment course may be repeated.

Refer to **Table 2** and **Table 3** and for a complete list of protocol required study assessments.

8-week treatment period may be initiated anytime from Day 1 to Day 122

[figure not shown]

Figure 1 WART 303 Study Diagram for Treatment

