14.3. Statistical Analysis of Efficacy

Unless otherwise stated, all efficacy summaries and analyses will be conducted using the ITT population. All efficacy summaries and analyses will be produced for the following groups:

- Subjects treated in the study that were randomized to active treatment during the previous A101-WART 301/302 study.
- Subjects treated in the study that were randomized to vehicle during the previous A101-WART 301/302 study.
- Subjects treated in the study overall.
- Subjects not requiring treatment during the study that were randomized to active treatment during the previous A101-WART 301/302 study.
- Subjects not requiring treatment during the study that were randomized to vehicle during the previous A101-WART 301/302 study.
- Subjects not requiring treatment in the study overall.
- All subjects combined

The primary efficacy analysis will be the effectiveness of A-101 45% based on the proportion of subjects who achieve complete clearance (PWA=0) of all identified common warts at any scheduled visit. Any identified common wart for a subject that has missing PWA data will be treated as not clear for the purpose of the primary efficacy analysis.

Four secondary efficacy analyses will be performed:

- Durability of response: for warts achieving a status of Clear (PWA=0), the number of weeks the wart remains clear will be tabulated and these results will be summarized using descriptive statistics. The proportion of these warts that remain clear at the end of the study will also be presented.
- Mean per-subject percent of treated warts that are Clear (PWA=0) at each visit will be summarized using descriptive statistics.
- Proportion of subjects with a single wart at baseline whose wart is Clear (PWA=0) will be summarized using descriptive statistics by visit.
- Median time to achieve onset of Clearance (PWA=0) for all treated warts.

Efficacy summaries will be supported by listings of PWA data.

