### 3. STATISTICAL METHODS

#### 3.1 Analysis Populations

The populations used for analyses are defined as follows:

- All Enrolled Population: The All Enrolled population includes all subjects that signed informed consent.
- Safety Population: The Safety population includes all subjects who received at least one application of study medication.

Enrollment, disposition, demographics, and baseline characteristics summaries will be presented for All Enrolled Population.

The Safety population will be used for both efficacy and safety analyses and summaries.

All subjects will be included in the listings.

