#### 3.2 Treatment Groups and Data Presentation

This is an open-label study with only one treatment arm. Subjects who enter the study with a common wart receive study medication immediately. Subjects who enter the study with no common warts do not receive study medication at the start and will not be treated at all if they do not develop any common warts throughout the course of the study. In order to be eligible for this study, subjects must have completed protocol treatment on either the A-101-WART-301 or A-101-WART-302 study. Both WART-301 and WART-302 were double-blind studies where subjects were treated with either active A-101 45% topical solution or vehicle solution. To best account for all potential exposure to A-101 45%, summaries and analyses will take into consideration both the current open-label treatment status as well as the randomized treatment assignment from the subject's respective double-blind study. This classification precipitates the following four treatment groups.

- Open Label A-101 45%: Double-Blind A-101 45%
- Open Label A-101 45%: Double-Blind Vehicle
- Open Label Not Treated: Double-Blind A-101 45%
- Open Label Not Treated: Double-Blind Vehicle

Depending upon analysis population, data will be summarized into all or a subset of treatment groups indicated above. Summaries on All Enrolled Population will display all four treatment groups. Summaries on Safety Population will display only first two treatment groups.

All data listings will be sorted by treatment group and subject ID. Subject ID will identify site number and double-blind study subject participated prior to open label study

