### **3.14 Changes in/ Clarifications to the Conduct of the Study or Planned Analysis**

Originally, both efficacy (primary and secondary endpoints) and safety analyses were planned on intent to treat (ITT) population. The primary objective of the study is to evaluate long-term safety of A-101 45% when applied twice weekly to common warts. Considering this and the fact that all treated subjects will administer the same medication (A-101 45%), it was deemed more appropriate to conduct both efficacy and safety analyses on the Safety Population. For that reason, all analyses will be conducted on the Safety Population. Data collected for subjects who did not receive treatment will be listed.

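### Durability of response is analysed only after open-label clearance: A-101-arm subjects who entered clear get no durability summary, and recurrences after Day 60 can be dated late

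*SAP*

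**What the plan says.** Duration of response is a secondary objective (Protocol 5.1.2, SAP 1.2). On subjects whose warts had all cleared by the end of the parent study, Protocol 6 says: "These subjects will be followed every 6 weeks to assess for a recurrence or development of new common warts". Protocol 14.3 lists, among the groups for all efficacy summaries, "Subjects not requiring treatment during the study that were randomized to active treatment during the previous A101-WART 301/302 study".

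The SAP changes the population. Section 3.10: "The primary and secondary efficacy analyses will be carried out on the Safety Population". Section 3.1: "The Safety population includes all subjects who received at least one application of study medication". Section 3.2: "Summaries on Safety Population will display only first two treatment groups". Section 3.14 discloses the change and adds: "Data collected for subjects who did not receive treatment will be listed". The reason given there is that the primary objective is safety and that all treated subjects use the same medication. It does not mention duration of response.

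The SAP durability endpoint is: "For subjects with all warts achieving a status of Clear (PWA=0), the number of weeks all warts remain clear", by treatment group and cycle. Section 3.10.2.1 analyses time to first recurrence with PROC LIFETEST, at study level and by cycle, and gives no rule for dating a recurrence.

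On assessments, Protocol 9.2 and Table 2 schedule the PWA on Days 1, 29, 60 and 182. The Table 2 calls on Days 102 and 144 ask about new warts (footnote 4). The Table 3 calls, for subjects who are clear, ask about both new warts and recurrence (footnote 2). Table 3 schedules no PWA.

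**The concern.** An A-101-arm subject who enters clear and stays clear has a durable response, and the six-weekly follow-up exists to observe it. Under the SAP that subject appears in no durability summary. One who enters clear, recurs and is treated joins the Safety Population, but the durability clock starts only at a later open-label clearance, so the time clear before re-treatment is not counted. The report would then address the duration-of-response objective for open-label clearances only.

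For the treated subjects who are analysed, the event of interest is the return of a treated wart. After Day 60 neither a scheduled examination nor the scripted call question looks for it until Day 182. A right-censored analysis that uses the detection date as the event date then overstates the weeks clear.

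**Working it through.** **1. The plan's own figure.** Protocol 14.1 and SAP 3.13: 400 subjects, 200 from the active arm, 26% clear. 200 x (1 - 0.26) = 148, which matches the stated number needing treatment. The complement is 200 x 0.26 = 52 entering clear.

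**2. How many subjects enter clear.** The 26% is described as a rate per wart, while entering clear means that every wart is clear. If warts clear independently (assumption), the number with m warts each is 200 x 0.26^m:
- m = 1: 52
- m = 2: 200 x 0.0676 = 13.5
- m = 3: 200 x 0.0176 = 3.5

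Positive correlation between warts in a subject would raise the last two. The documents give no distribution of warts per subject.

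**3. Share of clear follow-up time left out.** Share = E x 182 / (E x 182 + N x c x F), ignoring recurrences. E is the number entering clear. N is the number treated: (200 - E) prior-active plus 148 to 200 prior-vehicle (assumption). c is the proportion of treated subjects who clear, 0.2 to 0.4 (assumption). F is days clear to Day 182: 122 from a Day 60 PWA or 153 from a Day 29 PWA.

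| E | N | Lowest share | Highest share |
|---|---|---|---|
| 52 | 296-348 | 9464/(9464 + 348 x 0.4 x 153) = 31% | 9464/(9464 + 296 x 0.2 x 122) = 57% |
| 13.5 | 334.5-386.5 | 2457/(2457 + 386.5 x 0.4 x 153) = 9% | 2457/(2457 + 334.5 x 0.2 x 122) = 23% |
| 3.5 | 344.5-396.5 | 637/(637 + 396.5 x 0.4 x 153) = 3% | 637/(637 + 344.5 x 0.2 x 122) = 7% |

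The range is therefore about 3% to 57%.

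**4. The gap without a PWA.** For a course started on Day 1: 182 - 60 = 122 days (17.4 weeks). For a second course started on Day 60, its own Day 60 PWA falls on study Day 119: 182 - 119 = 63 days.

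**5. Size of late dating.** Take clearance at Day 60 and a constant hazard with p = 20/40/60% recurring by Day 182 (assumptions): S(t) = (1 - p)^(t/122).
- True mean time clear over 122 days = 122p/(-ln(1 - p)) = 109.3/95.5/79.9 days.
- Events dated at the calls (42 and 84 days after Day 60) or at Day 182: 42 + 42 x S(42) + 38 x S(84) = 113.5/104.0/92.9 days. The excess is 4.1/8.4/13.0 days (0.6/1.2/1.9 weeks). Divided by p, events are on average 20.7/21.1/21.6 days late.
- Events dated at Day 182 only: 122 days. The excess is 12.7/26.5/42.1 days (1.8/3.8/6.0 weeks). Events are 63.3/66.2/70.2 days late, or 61.0 if recurrences are spread evenly over the interval.

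**6. On the curve.** Ten weeks after clearance the true proportion clear is S(70) = 88/75/59%. Kaplan-Meier with call dates still reads S(42) = 93/84/73%. An interval-censored estimate places the value between S(42) and S(84), that is 93-86%, 84-70% and 73-53%, but does not identify it.

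**The case against.** The case against is substantial. Durability after open-label clearance is a legitimate target, the endpoint is secondary and descriptive in a safety study, and SAP 3.14 states the population change openly. All of that stands and limits the importance.

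A reader might infer that the population change alone removed this cohort and that returning to ITT would restore it. The documents do not support that. The protocol's durability measure also requires a wart to reach PWA=0, and Table 3 schedules no PWA. The group in Protocol 14.3 belongs to a general list for every efficacy summary; it is not a dedicated durability analysis.

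A reader might also infer that these subjects vanish from the report. They do not: enrolment, disposition and demographics are summarised in all four groups (SAP 3.1, 3.2), and their data are listed.

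A third tempting reading is that the entry-clear cohort offers far longer observation, since Protocol 4.2 says of the parent studies: "These studies will assess efficacy and safety of 8 weeks of treatment and 12 weeks of post treatment follow up". Time since double-blind treatment and time since open-label clearance are different clocks. A curve starting at WART-303 Day 1 spans 26 weeks, in subjects selected for still being clear.

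On dating, SAP Appendix A admits unscheduled visits, a separate data-handling document (SAP 3.11) may hold a rule, and a subject asked about new warts may mention one that has returned. Late dating is therefore a possibility whose extent cannot be fixed from these documents.

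**Conclusion.** The point holds in limited form. Followed as written, the SAP gives no durability summary for A-101-arm subjects who entered clear, although duration of response is an objective and they are followed for recurrence. The cause is the Safety Population restriction together with the absence of any PWA in Table 3. The omission may be trivial or large: about 3% to 57% of clear follow-up time, depending mainly on how the wart-level 26% translates to subjects and on assumed clearance in this study.

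Recurrences after Day 60 can be dated about 21 days late on average if the calls detect them, and 61-70 days late as an upper bound. The recurrence rates behind these figures are assumptions. The proportion clear at the end of the study does not depend on dating. Overall importance is minor to moderate; the changes are worth making because they are cheap.

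**What to change.** 1. Add one separate descriptive time-to-recurrence curve for entry-clear A-101-arm subjects, on the All Enrolled Population, with WART-303 Day 1 as origin and never-treated subjects censored at last contact. Do not pool it with open-label clearances. State beside it that it spans 26 weeks among subjects still clear at entry and that no PWA is scheduled for them. Table 3 marks Day 182 as an in-office visit while its footnote 2 lists a call that day; these must be reconciled, because they determine how final status is ascertained.
2. Add the Table 3 recurrence question to the Table 2 calls.
3. Report an interval-censored (Turnbull, PROC ICLIFETEST) estimate beside Kaplan-Meier, from last known clear to first known not clear. Note that it shows the range between contact days and does not recover the true value within them. State the event-date rule and whether a new wart counts as an event.

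The cost is SAP wording, one curve and one SAS procedure. The call question uses scheduled contacts but needs a small protocol amendment with IRB approval. The new curve will be imprecise: at 20% recurrence the Wilson 95% interval is about 11-33% with 52 subjects, and wider with fewer.

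As a separate point, the latest treatment start is Day 102 in the SAP Table 3 footnote and Day 122 elsewhere in the SAP and protocol. Those passages must be reconciled.

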### 3.10.2 Secondary Efficacy Analyses

#### 3.10.2.1 Durability of Response

Difference in time to recurrence of wart by treatment group is summarized using Kaplan Meier analysis. This analysis will be done at overall study level and by treatment cycle.

- **Overall Study Level:** Time to recurrence will be presented graphically with a Kaplan Meier curve. For this analysis, time to first recurrence in the study will only be included for each subject. Subjects with no wart at the end of study will be censored. The proportion of subjects that remain clear of warts at the end of the study will also be presented.
- **By Treatment Cycle:** For this analysis, time to first recurrence in the treatment cycle will only be included for each subject. Subjects with no wart at the end of the treatment cycle will be censored.

Kaplan-Meier estimates and associated confidence intervals are obtained using SAS statements consistent with the following syntax:

```
PROC LIFETEST ALPHA=.05;  
  TIME DAYS*CENSOR(1);  
  SURVIVAL OUT=SURV CONFTYPE=LOGLOG;  
  STRATA TREATMENT GROUP;
```

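### The SAP moves durability of response from the wart to the subject without recording the change, so the protocol's wart-level durability result is not produced

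*SAP*

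**What the plan says.** Duration of response is a secondary objective in both documents (Protocol 5.1.2, SAP 1.2).

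Protocol 14.3 makes the wart the unit: "for warts achieving a status of Clear (PWA=0), the number of weeks the wart remains clear will be tabulated", summarised with descriptive statistics. It adds an end-of-study result on the same unit: "The proportion of these warts that remain clear at the end of the study will also be presented".

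SAP 3.10 makes the subject the unit and sets an entry condition: "For subjects with all warts achieving a status of Clear (PWA=0), the number of weeks all warts remain clear", reported for each treatment group and cycle.

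SAP 3.10.2.1 uses Kaplan-Meier with one time per subject. At overall study level, "time to first recurrence in the study will only be included for each subject"; by cycle, "time to first recurrence in the treatment cycle will only be included for each subject". Its end-of-study result also counts subjects: "The proportion of subjects that remain clear of warts at the end of the study will also be presented".

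SAP 3.14 records one change, the move away from the ITT population, and ends: "For that reason, all analyses will be conducted on the Safety Population". It says nothing about durability. The SAP introduction names protocol Version 3 as the version it implements, so the wart-level definition is current protocol text.

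**The concern.** Three things differ between the two definitions: the unit (wart or subject), the set that qualifies (any cleared wart, or only subjects whose warts are all clear), and the summary (descriptive weeks clear, or Kaplan-Meier time to first recurrence). None is recorded as a change.

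Partial response is built into the design. Up to six warts may be treated in a course (Protocol 9.1), and application stops wart by wart as each clears (Protocol 9.2). Under SAP 3.10, a cleared wart on a subject with one persisting wart adds nothing to the durability result. No other planned summary fills the gap: the per-subject percentage of warts clear (SAP 3.10.2.2) shows status at each visit, not how long a wart stays clear. At stake is what the trial reports for a stated secondary objective. Efficacy is descriptive with no formal test (SAP 3.10.1), so no error rate is involved.

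**Working it through.** **Effect on one subject.** Take three treated warts. Two are clear at Day 29 and still clear at Day 182; the third never clears.
- Protocol 14.3: two durations of (182 − 29)/7 = 21.9 weeks, and 2 of 2 cleared warts still clear.
- SAP 3.10: the subject does not qualify, so no duration.

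**Inputs for the size.**
- Warts per course: 1 to 6 (Protocol 9.1).
- Per-wart clearance p = 0.26, the figure expected at the end of the parent studies (Protocol 14.1). The plan's own arithmetic with it reproduces: 200 × (1 − 0.26) = 148. Applying it to a course in this study is an assumption, so p = 0.50 is also shown.
- Within-subject correlation ρ and the distribution of wart counts are not in the documents. Both are assumed.

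**Formulas.** For a subject with k warts, using a beta-binomial model:
- A(k) = P(all k clear) = product over i = 0 to k − 1 of [p(1 − ρ) + iρ] / [(1 − ρ) + iρ]. With ρ = 0 this is p^k.
- Share of cleared warts excluded = 1 − A(k)/p. For k = 2 this reduces to (1 − p)(1 − ρ).
- Pooled over wart counts with weights w(k): 1 − Σ w(k)·k·A(k) / [p·Σ w(k)·k].

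**Results: share of cleared warts excluded by the all-clear rule.**

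| Wart count | p | ρ = 0 | ρ = 0.3 | ρ = 0.7 |
|---|---|---|---|---|
| k = 1 | any | 0% | 0% | 0% |
| k = 2 | 0.26 | 74% | 52% | 22% |
| k = 2 | 0.50 | 50% | 35% | 15% |
| k = 6 | 0.26 | 99.9% | 89% | 46% |
| k = 6 | 0.50 | 97% | 75% | 34% |
| Uniform 1–6 | 0.26 | 91% | 76% | 38% |
| Uniform 1–6 | 0.50 | 82% | 61% | 27% |
| Skewed 40/25/15/10/5/5% | 0.26 | 75% | 60% | 29% |
| Skewed 40/25/15/10/5/5% | 0.50 | 64% | 46% | 20% |

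The 15% is (1 − 0.50)(1 − 0.7), for two-wart subjects. The 91% is the uniform case at p = 0.26 and ρ = 0: Σ k·0.26^k = 0.474, divided by 0.26 × 21 = 5.46, gives 8.7% retained. These are illustrations, not bounds. The share falls towards zero as more subjects have a single wart, and exceeds 91% if most have many warts.

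**Resolution of the durations.** PWA is scheduled at Days 1, 29, 60 and 182 (Protocol 9.2). For a wart first scored clear at Day 60, with no further course, the next scheduled PWA is 182 − 60 = 122 days (17.4 weeks) later. Any recurrence in that gap is known only to lie within it, under either definition.

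**The case against.** The strongest defence is that a subject-level endpoint is a coherent choice. The primary efficacy endpoint is complete clearance per subject in both documents, a subject-level duration follows from it, and it avoids the clustering of warts within subjects, which Protocol 14.3 does not address. Protocol 14 leaves detail to the SAP, the study is an open-label safety study, and PWA listings would let someone derive wart-level durations later. All of that supports keeping the subject-level analysis. It does not make a change of unit and qualifying set a detail, and a listing is not the summary that the protocol promises.

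The all-clear condition also appears only in SAP 3.10. Section 3.10.2.1 does not repeat it, and defines neither the time origin nor recurrence. A partial responder might therefore enter the Kaplan-Meier analysis on some reading. This stands as an ambiguity, but one time per subject still removes wart-level durations.

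A reader might infer two stronger points that the documents do not support. One is that the SAP result rests on only a minority of cleared warts. That depends on wart counts and correlation that the documents do not give; in several scenarios above most are retained. The other is that durability will look too good. Restricting to all-clear subjects may favour longer durations, but ending the clock at the first recurrence of any wart shortens them: if one of six cleared warts returns, the protocol still counts five as clear, while the SAP counts a recurrence. The net direction is unknown.

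**Conclusion.** The concern holds as an unrecorded change of endpoint. The wart-level weeks clear and the proportion of cleared warts still clear at the end of the study, both specified in Protocol 14.3, are not produced under the SAP. Cleared warts on subjects with a persisting wart contribute no duration. This part rests on the text alone.

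The size does not. The 15% to 91% depends on assumed clearance, correlation and wart counts, and shows only that the loss could be small or large. Subjects with one treated wart are unaffected. No sample size, power or error rate changes. The point should be addressed because it alters the reported answer to a secondary objective.

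**What to change.** In SAP 3.10 and 3.10.2.1, restore the protocol's wart-level summary: weeks clear for each wart reaching PWA=0, and the proportion of those warts still clear at the end-of-study visit, with confidence intervals clustered by subject. State that recurrence times are interval-censored between scheduled PWA visits, and that a wart with no later PWA is censored at its last PWA. The second rule is needed because warts are identified per treatment period, and the documents do not say whether a wart cleared in one course is still scored in later ones.

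Keep the subject-level Kaplan-Meier analysis as an additional analysis, and log the difference from Protocol 14.3 in SAP 3.14.

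The cost is one extra table. PWA is already scored for each identified wart, and each wart is marked on body charts (Protocol 9.1 and 9.2), so no new assessment is needed. The drawback is that the durations will be coarse.
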